#### **11.4.2. Overdose**

An overdose is any dose of study treatment administered to a subject or taken by a subject that exceeds the dose assigned to the subject according to the protocol. Overdoses are not considered AEs and should not be recorded as an AE on the eCRF; however, all overdoses must be recorded on an Overdose form and faxed or emailed to the Sponsor within 24 hours of the site becoming aware of the overdose. An overdose must be reported to the Sponsor even if the overdose does not result in an AE. If an overdose results in an AE, the AE must be recorded. If an overdose results in an SAE, both the SAE and Overdose forms must be completed and faxed or emailed to the Sponsor. All study treatment-related dosing information must be recorded on the dosing eCRF.

#### **11.4.3. Medical Emergency**

In a medical emergency requiring immediate attention, site staff will apply appropriate medical intervention, according to current standards of care. The Investigator (or designee) should contact the study's Medical Director. Refer to the Study Reference Manual's Official Study Contact List for complete contact information.

### **11.5. Contraception Requirements**

All male and female subjects must agree to the use of 2 methods of contraception for the duration of the study and 30 days after the final dose of study treatment. This includes at least 1 form of highly effective method of contraception and 1 acceptable method of contraception (and additional restrictions, if required, will be clarified in the locally approved ICF). Subjects who are abstinent are eligible, provided they agree to the use of 2 contraceptive methods (at least 1 being a highly effective method) should they become sexually active.

#### **Highly effective methods may include:**

- Oral, intravaginal, or transdermal combined (estrogen and progestogen containing) hormonal contraception associated with inhibition of ovulation (oral contraceptives must have been initiated at least 30 days prior to screening)
- Oral, injectable, or implantable progestogen-only hormonal contraception associated with inhibition of ovulation (oral contraceptives must have been initiated at least 30 days prior to screening)
- Intrauterine device
- Intrauterine hormone-releasing system
- Bilateral tubal occlusion
- Vasectomized partner (provided that partner is sole sexual partner of subject and partner has received medical assessment of surgical success)

CONFIDENTIAL

The information contained herein may not be used, disclosed, or published without the written consent of Biogen MA Inc.

- Sexual abstinence (defined as refraining from heterosexual intercourse during the entire study period through at least 30 days after the final dose of study treatment)

**Acceptable methods may include:**

- Double-barrier protection (e.g., male condom, female condom, cervical cap or contraceptive sponge with spermicide, or a diaphragm with spermicide)

Subjects who are surgically sterile are exempt from the requirement to use contraception. Women who have undergone a documented complete hysterectomy, bilateral tubal ligation, or bilateral salpingo-oophorectomy at least 6 months prior to screening are considered surgically sterile. Men who have undergone a vasectomy are considered surgically sterile as long as medical confirmation of azoospermia is provided. Women who are postmenopausal are also exempt from the requirement to use contraception. For the purpose of this study, postmenopausal is defined as the permanent cessation of menstruation for at least 12 months prior to screening in women who are 45 years of age or older.

If any female subjects become or is found to be pregnant while participating in the study, she will be discontinued from study treatment immediately. Pregnancies in female subjects and female partners of male subjects should be handled in the same manner. The Investigator must fill out a Pregnancy Report Form and submit the information to the Sponsor within 24 hours of awareness of the pregnancy, irrespective of whether an AE has occurred. The ET and safety follow-up visits will be scheduled.

The Investigator will follow the pregnancy until completion or until pregnancy termination and notify the outcome to the Sponsor. If the outcome of the pregnancy meets the criteria for immediate classification as an SAE the Investigator should follow the procedure of reporting SAEs (see Section 11.3.3). Additional follow-up may be required.

Pregnancy reporting is described in Section 11.4.1.

## **11.6. Safety Responsibilities**

### **11.6.1. The Investigator**

The Investigator's responsibilities include the following:

- Monitor and record all AEs, including SAEs, on the eCRF regardless of the severity or relationship to study treatment.
- Determine the seriousness, relationship, and severity of each event.
- Determine the onset and resolution dates of each event.
- Monitor and record all pregnancies and follow up on the outcome of all pregnancies.

CONFIDENTIAL

The information contained herein may not be used, disclosed, or published without the written consent of Biogen MA Inc.

- Complete an SAE form for each SAE and fax or email it to the Sponsor within 24 hours of the site staff becoming aware of the event.
- Pursue SAE follow-up information actively and persistently. Follow-up information must be reported to the Sponsor within 24 hours of the site staff becoming aware of new information.
- Ensure all AE and SAE reports are supported by documentation in the subjects' medical records.
- Pursue AE follow-up information, if possible, until the event has resolved or become stable. Record AE follow-up information, including resolution, on the eCRF, as applicable.
- Report SAEs to local ethics committees, as required by local law.

#### **11.6.2. The Sponsor**

The Sponsor's responsibilities include the following:

- Before a site can enroll any subjects, the Clinical Monitor (or designee) is responsible for reviewing with site staff the definitions of AE and SAE, as well as the instructions for monitoring, recording, and reporting AEs and SAEs.
- The Sponsor is to notify all appropriate regulatory authorities, central ethics committees, and Investigators of SAEs, as required by local law, within required time frames.

CONFIDENTIAL

The information contained herein may not be used, disclosed, or published without the written consent of

Biogen MA Inc.

## **12. STATISTICAL METHODS AND DETERMINATION OF SAMPLE SIZE**

The objectives of the study and the endpoints to be analyzed are listed in Section [4](#).

### **12.1. General Considerations**

The statistical analysis methods are described below. Additional details will be provided in the Statistical Analysis Plan.

In general, summary statistics (number of subjects, mean, standard deviation, median, minimum, and maximum values for continuous variables, and number and percentage of subjects in each category for categorical variables) will be provided for all parameters. All statistical results will be presented based on observed values. All individual subject level data will be presented as data listings.

### **12.2. Analysis Sets**

#### **12.2.1. Safety Population**

The safety population, defined as all enrolled subjects who receive at least 1 dose of ALKS 8700, will be used in the safety analyses.

#### **12.2.2. Efficacy Population**

The exploratory efficacy endpoints to assess treatment effect over time will be analyzed using data from the full analysis set (FAS), defined as all subjects who receive at least 1 dose of ALKS 8700 and receive 1 postbaseline efficacy assessment.

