### **5.4. Unscheduled Visits**

Data collected during unscheduled visits should be recorded in electronic case report forms (eCRFs) only if the data support protocol objectives and/or are required for safety monitoring.

CONFIDENTIAL

The information contained herein may not be used, disclosed, or published without the written consent of Biogen MA Inc.

An Unscheduled Relapse Visit will be conducted in the event of a suspected relapse (Section 7.2.2). This visit should occur as early as possible but within 7 days of the onset of the potential relapse. The following assessments will be made:

- Physical examination
- Concomitant medication review
- AE monitoring
- Urine pregnancy test
- Vital signs
- Safety laboratory assessments
- Relapse assessment
- EDSS

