## **8. DISCONTINUATION OF STUDY TREATMENT AND WITHDRAWAL OF SUBJECTS FROM THE STUDY**

### **8.1. Discontinuation of Study Treatment**

A subject *must* permanently discontinue ALKS 8700 for any of the following reasons:

- The subject becomes pregnant. Study treatment must be discontinued immediately. Report the pregnancy according to the instructions in Section 11.4.1.
- The subject withdraws consent to continue study treatment.
- The subject experiences an AE that necessitates permanent discontinuation of study treatment.
- At the discretion of the Investigator for medical reasons.

The primary reason for discontinuation of study treatment must be recorded in the subject's eCRF.

Any subject who prematurely discontinues from either study treatment or the study will be asked to return to the clinic for an ET visit (Visit 15) as well as a safety follow-up visit 2 weeks later (Visit 16) for the required assessments. Please see Section 5.5 for the follow-up of subjects with lymphopenia.

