### 8.3. Withdrawal of Subjects From the Study

A treatment completer will be a subject who completes the 96-week treatment period (i.e., through Visit 15). Subjects completing the follow-up visit will be categorized as completing the study.

A subject may be withdrawn from the study at any time if the subject, Investigator, or Sponsor determines that it is not in the best interest of the subject to continue participation. Reasons for discontinuation include:

- AE
- Lack of efficacy
- Lost to follow-up
- Withdrawal by subject
- Protocol deviation (noncompliance with study treatment or study procedures)
- Physician decision
- Pregnancy
- Study terminated by Sponsor
- Other

If a subject withdraws from the study for any reason, any ongoing AEs will be followed until resolution, until deemed stable by the Investigator, or until the subject is deemed by the Investigator to be lost to follow-up. If, in the opinion of the Investigator, it is necessary to monitor a subject beyond the safety follow-up visit, the follow-up period may be extended as necessary. In such instances, the Sponsor and the Investigator will agree to an acceptable follow-up schedule. If a subject withdraws from the study and has a last lymphocyte count which is  $< 0.8 \times 10^3/\mu\text{L}$ , the subject will return to the clinic for additional lymphocyte count monitoring visits every 2 months starting from the safety follow-up for up to 6 months (i.e., a maximum of 3 visits) or until the lymphocyte count reaches normal limits ( $\geq 0.91 \times 10^3/\mu\text{L}$ ), whichever occurs first.

In the event that a subject chooses to withdraw from the study, the Investigator should make a reasonable effort to ascertain the reason(s) for withdrawal, while fully respecting the subject's rights. Subjects discontinuing study treatment and withdrawing from the study are to be asked to return to the clinic for an ET visit. The ET visit should be scheduled as close as possible to the subject's last dose and will mimic the assessments scheduled to be conducted at Visit 15. Following the ET visit, subjects will be asked to participate in the safety follow-up period. If the subject fails or refuses to return to the study site, an attempt must be made to contact the subject

CONFIDENTIAL

The information contained herein may not be used, disclosed, or published without the written consent of

Biogen MA Inc.

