by telephone in order to assess as many safety and efficacy parameters as possible. All data collected over the telephone must be documented and kept in the subject's record.

The Investigator must maintain a record of all subjects who fail to complete the study. The reason for study discontinuation will be documented and made on the appropriate eCRF. If a subject is lost to follow-up, a reasonable attempt to contact the subjects must be made and documented.

Subjects who withdraw from the study after receiving the first dose of study treatment may not be replaced.

CONFIDENTIAL

The information contained herein may not be used, disclosed, or published without the written consent of  
Biogen MA Inc.

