3.1.1.2. Efficacy Population

The efficacy endpoints to assess treatment effect over time will be analyzed using data from the Full Analysis Set (FAS), defined as all subjects who receive at least one dose of ALKS 8700 and have had at least one post-baseline efficacy assessment.

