3.5. Efficacy Analyses

3.5.1. General Considerations

All efficacy analyses will be carried out using the FAS population. For rollover subjects, efficacy assessment in the antecedent ALK8700-A302 study will be carried over as baseline if visit 2 in current study is not collected. All efficacy endpoints will be summarized by enrollment group and overall. Supportive listings will be provided.

[REDACTED]

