The date of the initial EDSS assessment at which the minimum increase in the EDSS is met will be the date of onset of the progression (tentative progression). The progression is defined as confirmed when this minimum EDSS change is present on the next study visit occurring after 12 weeks or longer from the onset of the progression. EDSS assessments within 30 days after a protocol-defined relapse will not be used for confirmation of disability progression. If a subject meets the defined criteria of confirmed progression and is also having a relapse, the subject will be required to meet the defined minimum criteria at the subsequent visit.

Death due to MS before a confirmed disability progression will be counted as progression. If the subject was in the midst of a tentative progression at the time of death (e.g. the EDSS evaluation prior to death is a tentative progression), the progression date will be the date of the onset of the progression. Otherwise, the progression date will be the date of death.

Subjects who do not have a confirmed progression based on the above rules will be censored. The censor date will be the date of the last EDSS assessment in the study, unless the subject was in the midst of a tentative progression. For subjects with a tentative progression at the last study visit, the censor date will be the date of the onset of the progression. Subjects who withdraw from the study after the baseline visit but prior to the first clinical evaluation scheduled visit will be censored at baseline.

Estimated proportion of subjects with 12-week confirmed progression at 48, 60, 72, 84, and 96 weeks will be calculated with the use of the Kaplan–Meier product-limit method and reported by enrollment group and overall.

Timed 25-foot walk (T25-FW) score

The T25-FW is a reliable quantitative mobility and leg function performance test based on a timed 25-foot walk (T25-FW). The subject is directed to one end of a clearly marked 25-foot course and is instructed to walk 25 feet as quickly as possible, but safely. Subjects are allowed to use assistive devices (canes, crutches, walkers) as needed. The time is calculated from when the lead foot crosses the start point to when the subject has reached the 25-foot mark. The task is immediately administered again by having the subject walk back the same distance. The score for the T25-FW is the average of the two completed trials.

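### Among subjects who leave before Day 85 with no early-termination assessment, entry to the efficacy set depends on whether a suspected relapse was examined, which slightly inflates the mean individual relapse rate

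*Protocol*

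**What the plan says.** Protocol 12.2.2 defines the FAS as "defined as all subjects who receive at least 1 dose of ALKS 8700 and receive 1 postbaseline efficacy assessment". SAP 3.1.1.2 sets the same condition: subjects must "have had at least one post-baseline efficacy assessment". Neither document says which assessments count. SAP 3.5.1 states: "All efficacy analyses will be carried out using the FAS population". That covers the relapse frequency table, the Kaplan-Meier relapse proportion at Week 96, the group ARR, and the mean and median of individual relapse rates in SAP 3.5.3.

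In the readable schedules (Table 1 of each document) the first EDSS and timed 25-foot walk after dosing are at Visit 6, Day 85. The SF-12 and EQ-5D-5L first follow at Visit 9, Day 169. Three routes can produce efficacy data earlier:

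- **Suspected relapse.** Protocol 5.4: "An Unscheduled Relapse Visit will be conducted in the event of a suspected relapse". That visit includes an EDSS.
- **Early termination.** Protocol 8.1 says a subject who stops treatment or the study early "will be asked to return to the clinic for an ET visit (Visit 15"). Under protocol 8.3 this visit "will mimic the assessments scheduled to be conducted at Visit 15", which include the EDSS, timed walk, SF-12 and EQ-5D-5L.
- **Telephone.** If the subject does not return, protocol 8.3 requires an attempt at contact "by telephone in order to assess as many safety and efficacy parameters as possible".

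**The concern.** Attendance at the early-termination visit is requested, and protocol 8.2 and 8.3 foresee subjects who refuse or cannot be reached. For an early leaver with no such visit, the remaining sure route into the FAS is an examination for a suspected relapse. Membership of the analysis set then depends on the outcome being counted: relapse-free early leavers and their follow-up time drop out, while those examined for a relapse stay.

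The summary most exposed is the mean of individual relapse rates, because it gives every subject equal weight. One relapse in 30 days of follow-up scores 365.25/30 = 12.2 per year, and the zeros that should balance it are the values removed.

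The effect probably falls mainly on De Novo Subjects. Under protocol 12.3 the baseline of Rollover Subjects lies in the antecedent study, so assessments made there might already count as post-baseline. SAP 3.5.1 describes their baseline differently, so this is not settled.

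**Working it through.** The plan gives no relapse rate, dropout rate or early-termination attendance, so there is no planned figure to reproduce. The visit arithmetic agrees with the schedule: Week 12 is 12 × 7 + 1 = Day 85.

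**Inputs.** From the documents: N = 1000 (approximately), first scheduled EDSS at Day 85, Week 96 at Day 673. Assumed: true rate λ of 0.1, 0.2 or 0.4 per year; share p leaving before Day 85 of 3%, 8% or 15%; early-termination attendance a of 0%, 50%, 90% or 100%; exit times uniform; a further 20% leaving later; every early relapse examined; telephone data not counted.

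**Step 1, subjects dropped.** Mean follow-up of an early leaver is about 42/365.25 = 0.115 years.

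D = N × p × (1 − a) × (1 − 0.115λ)

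With p = 8%, a = 50%, λ = 0.2: D = 1000 × 0.08 × 0.5 × 0.977 = 39.1.

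**Step 2, mean individual rate.** Each dropped subject contributes zero to the sum of rates, so the sum is unchanged and only the divisor shrinks.

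Relative increase = D/(N − D) = 39.1/960.9 = 4.1%.

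**Step 3, pooled ARR.** Relapses are unchanged, and the patient-years lost are 39.1 × 0.115 = 4.5. Taking the later leavers as 20% of all subjects, total patient-years are 80 × 0.115 + 200 × (378/365.25) + 720 × (672/365.25) = 9 + 207 + 1325 = 1541.

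Relative increase = 4.5/(1541 − 4.5) = 0.29%.

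**Step 4, simulation of the same set-up** (300 trials of 1000 subjects per scenario). For the example above, all dosed versus FAS:

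- mean individual rate 0.1975 versus 0.2055 (+4.1%)
- pooled ARR 0.1998 versus 0.2003 (+0.29%)
- Kaplan-Meier proportion at Week 96 30.76% versus 30.83% (+0.07 points)

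Increase from all dosed to FAS, over λ = 0.1 to 0.4:

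| Attendance | Early exit | Mean individual rate | Pooled ARR | Kaplan-Meier (points) |
|---|---|---|---|---|
| 0% | 3% | 2.9–3.0% | 0.20–0.21% | 0.03–0.06 |
| 0% | 8% | 8.3–8.6% | 0.57–0.59% | 0.08–0.19 |
| 0% | 15% | 16.7–17.4% | 1.15–1.21% | 0.18–0.38 |
| 50% | 3% | 1.5% | 0.10–0.11% | 0.01–0.03 |
| 50% | 8% | 4.0–4.1% | 0.29–0.30% | 0.04–0.09 |
| 50% | 15% | 7.7–7.9% | 0.57–0.60% | 0.08–0.18 |
| 90% | 15% | 1.5% | 0.11–0.12% | 0.01–0.04 |
| 100% | any | 0 | 0 | 0 |

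A separate simulation with λ = 0.15 agrees. Early exit of 5% with 70% attendance moved the mean individual rate from 0.1501 to 0.1523 (+1.5%). Early exit of 10% with 50% attendance moved it from 0.1504 to 0.1581 (+5.1%).

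**The case against.** A reader might infer that early leavers as a class are kept if they relapsed and dropped if they did not. The documents do not support that. Every early leaver is asked to attend a visit with the full set of efficacy scales, so a relapse-free subject who attends is in the FAS. A suspected relapse that is not confirmed also yields an EDSS, and a relapse that is never reported yields none. Nor can one say that the FAS excludes most early leavers, because that share depends on an attendance figure the documents do not give.

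The premise itself has some give. Because the qualifying assessment is undefined, and protocol 9.1 lists MS relapse among the clinical efficacy assessments, routine relapse follow-up before Day 85 could be read as sufficient. Telephone data might count too, although an EDSS based on examination and a timed walk cannot readily be done by telephone. Redacted schedule rows may hold another early assessment. Any of these would shrink the effect or remove it.

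A protocol-defined relapse needs an examination, so relapse endpoints require more than dosing dates and follow-up time. Counting unexamined early leavers as relapse-free could miss relapses and bias the rate downward. This stands as a small cost, but the plan already counts follow-up without an examination for subjects inside the FAS.

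It is also tempting to see a conflict with SAP 3.5.3, which says of confirmed progression: "Subjects who withdraw from the study after the baseline visit but prior to the first clinical evaluation scheduled visit will be censored at baseline". The rule can still act on early leavers who qualify for the FAS, and subjects censored at time zero add nothing to a Kaplan-Meier estimate. No change is needed there.

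Finally, these endpoints are exploratory, single-arm and descriptive, with no formal comparison of enrollment groups. That limits the consequence without justifying the exclusion.

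**Conclusion.** The point holds for a defined subset: subjects who leave before Day 85 with no early-termination assessment. For them, entry to the FAS can depend on the outcome. The direction is upward, so relapse is overstated and the drug is not flattered.

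For pooled ARR and the Kaplan-Meier proportion the effect is negligible: at most 0.6% and 0.18 points with half of early leavers attending. For the mean individual rate it is about 1.5% (3% early exit with 50% attendance, or 5% with 70%) to 8% (15% with 50%). By the formula above, 3% early exit with 70% attendance gives 8.8/991.2 = 0.9%. At full attendance it is zero.

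All exit, attendance and relapse figures are assumptions. Concentration in De Novo Subjects is likely but cannot be sized, since their number is not given. The rule in protocol 7.2 that ends participation around Visit 4 makes early exits foreseeable, but those subjects are identified near a clinic visit, so it is weak evidence of missed assessments. This is a minor improvement to the plan; no main conclusion is threatened.

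**What to change.** In SAP 3.5.1, with a matching line in protocol 12.2.2:

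- Analyze relapse frequency, ARR (group and individual) and Kaplan-Meier time to relapse in all subjects who receive at least one dose, with follow-up time as already defined. This set exists as the Safety Population.
- Keep the FAS for change-from-baseline endpoints.
- Report how many dosed subjects fall outside the FAS, by enrollment group.

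The change takes a few lines of text and no new data. It has two small costs: relapse tables will have a different denominator from the other efficacy tables, and short follow-up without a final examination will count as relapse-free.
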